6.2 Pediatric Migraine Disability Assessment Questionnaire

The PedMIDAS was developed based on the adult migraine disability assessment and measures the effect of migraine headaches on school absence, functioning during school, and disruption of home and social/recreational activities. It is the only instrument designed and validated to assess migraine disability in pediatric and adolescent patients (Hershey et al., 2001), and has been validated for the age range of 4 to 18 years.

The PedMIDAS ([Appendix 10.3](#)) is a publicly available tool that evaluates the impact of headaches on school, home, play, and social activities. It is comprised of 6 questions related to the impact of headache on school performance such as number of days missed in various activities over the past 90 days (Questions 1-3). The fourth question concerns the disability at home, while the last two questions relate to social and sport activities. The Headache Disability Score is a composite of the values for the 6 questions, where a total disability score of 0 to 10 = Little to no disability;

This document is confidential. It contains proprietary information of Supernus® Pharmaceuticals, Inc. Any viewing or disclosure of such information that is not authorized in writing by the Sponsor is strictly prohibited. Such information may be used solely for the purpose of reviewing or performing this study.

11 to 30 = Mild disability; 31 to 50 = Moderate disability; and >50 = Severe disability. The ratings for two additional prompts for Headache Frequency and Headache Severity are not included in the Headache Disability Score but are used for clinical reference.

The questionnaire is self-administered by the subject and may be completed in collaboration with the subject's parent or caregiver, as long as the answers are confirmed by the subject.

The PedMIDAS will be administered at the Screening Visit, Visit 3, Visit 5, Visit 8 and Visit 9.

6.3 Pediatric Quality of Life Inventory, Version 4.0

The PedsQL 4.0 is a generic measure of HRQoL that has been developed for use with children 2 to 18 years of age (Varni, Seid, & Rode, 1999). The questionnaire allows a comparison of QoL effects across acute and chronic health conditions and with healthy children and is available as child self-report and parent-proxy report. The measure has been validated in patient populations with cancer, rheumatoid disease, diabetes, and orthopedic conditions, as well as in children ages 7 to 12 years with a recurrent headache symptom.

The PedsQL 4.0 (Appendix 10.4) has two forms: a child self-report and a parent-report form. The child self-report includes 3 age ranges for young children (5-7 years), children (8-12 years), and adolescents (13-18 years). The PedsQL scale consists of 23 items (questions) comprising four areas of functioning, including physical (8 items), emotional (5 items), social (5 items), and school (5 items). The items are assessed based on the recall interval of 1 month and are scored on a 5-point Likert scale of 0 to 4, where 0 = Never; 1 = Almost never; 2 = Sometimes; 3 = Often; and 4 = Almost always.

The PedsQL 4.0 will yield a total score, 2 summary scores, (the Physical Health Summary Score and the Psychosocial Health Summary Score) and 3 sub-scores (Emotional, Social and School Functioning). The Psychosocial Health Summary Score is a composite of the scores from the Emotional, Social and School Functioning scales; the Physical Health Summary Score is the same as the Physical Functioning scale score.

To obtain the total score, the items are reverse-scored and linearly transformed (0 = 100, 1 = 75, 2 = 50, 3 = 25, and 4 = 0) to a scale that ranges from 0 (worst HRQoL) to 100 (best HRQoL). The Total Scale Score is the sum of all the items in all the scales.

The parent and child should be completing their respective questionnaires independently of each other.

The PedsQL 4.0 will be administered at Visit 3, Visit 5, Visit 8 and Visit 9.

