2.6 Secondary Endpoints

The secondary efficacy endpoints are:

1. Responder, defined as a subject with $\geq 50\%$ reduction in the MMDs during the last 4 weeks of the Treatment Phase relative to Prospective Baseline Period.

2. Change from baseline in the monthly migraine-specific acute rescue medication use in the last 4 weeks of the Treatment Phase.
3. Change in the monthly rate of total headache days (migraine and non-migraine), duration and severity.
4. Change in the time to onset of action, defined as the time to first statistically significant treatment effect observed and maintained until the EOS.
5. Change from baseline in the Headache Disability Score as measured by PedMIDAS during the last 4 weeks of the Treatment Phase.
6. Change from baseline in the HRQoL as measured by the PedsQL 4.0 Total Scale Score during the last 4 weeks of the Treatment Phase for the self-report and the parent-report.

The safety endpoints are:

1. Incidence of AEs.
2. Clinical laboratory test results (blood chemistry and hematology, urinalysis).
3. Vital signs, physical and neurological examinations, and ECGs.
4. C-SSRS assessment.
5. Cognitive Assessment.

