6. HRQoL: The change from baseline in the HRQoL as measured by the PedsQL4.0 Total Scale Score during the last 4 weeks of the Treatment Phase for the self-report and the parent-report will be summarized using descriptive statistics by visit.

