### 5.2. Secondary Efficacy Variables

The secondary efficacy endpoints are:

1. Responder, defined as a subject with  $\geq 50\%$  reduction in the MMDs during the last 4 weeks of the Treatment Phase relative to Prospective Baseline Period.
2. Change from baseline in the monthly migraine-specific acute rescue medication use in the last 4 weeks of the Treatment Phase.

The 28-day rate of migraine-specific acute rescue medication (MED) days is calculated during the last 4 weeks of DBL period as

$$\frac{\# \text{ of days rescue MED used}}{\# \text{ of days with nonmissing headache record in the diary}} \times 28$$

The 28-day rate for the prospective baseline is calculated as in above during the 4 weeks

of ‘prospective baseline’.

3. Change in the monthly rate of total headache days (migraine and non-migraine), duration and severity.
  - a) Total headache days: The 28-day rate of total headache days and prospective baseline are calculated using the same formula as for the primary endpoint.
  - b) Duration of headache: The 28-day duration is calculated during the last 4 weeks of DBL period as

$$\frac{\text{sum of all headache duration}}{\# \text{of days with nonmissing headache record in the diary}} \times 28$$

The 28-day rate for the prospective baseline is calculated as in above during the 4 weeks of ‘prospective baseline’.

- c) Severity of headache: The 28-day rate for severity will be calculated for each headache incidence of severity category (mild, moderate, severe, and very severe). The 28-day rate for mild severity is calculated during the last 4 weeks of DBL period as:

$$\frac{\# \text{of days with mild headache incidence}}{\# \text{of days with nonmissing headache record in the Diary}} \times 28$$

The 28-day rate for the prospective baseline is calculated as in above during the 4 weeks of ‘prospective baseline’.

The 28-day rates of moderate, severe, and very severe headache days will be calculated similarly.

4. Onset of treatment effect, defined as the time to first statistically significant treatment effect observed and maintained until the end of study in the primary endpoint.
5. Change from baseline in the Total Headache Disability Score as measured by PedMIDAS during the last 4 weeks of the Treatment Phase.
6. Change from baseline in the HRQoL as measured by the PedsQL 4.0 Total Scale Score during the last 4 weeks of the Treatment Phase for the self-report and the parent-report.

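### Protocol Section 6.3 defines the PedsQL Total Scale Score as a sum of 23 items each scored 0–100, which gives 0–2300 and not a score on the 0–100 scale just described

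*Protocol*

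**What the plan says.** Protocol Section 6.3 describes the instrument: "The PedsQL scale consists of 23 items (questions) comprising four areas of functioning". Physical functioning has 8 of them; the emotional, social and school domains have 5 each. The recoding of responses is given next: "the items are reverse-scored and linearly transformed (0 = 100, 1 = 75, 2 = 50, 3 = 25, and 4 = 0"). That same sentence places the recoded values on fixed limits: "to a scale that ranges from 0 (worst HRQoL) to 100 (best HRQoL"). Then comes the rule for combining them: "The Total Scale Score is the sum of all the items in all the scales".

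The score is a named secondary endpoint. Protocol Section 2.6 lists "Change from baseline in the HRQoL as measured by the PedsQL 4.0 Total Scale Score during the last 4 weeks of the Treatment Phase", covering child and parent forms, and SAP Section 5.2, item 6, repeats it: "Change from baseline in the HRQoL as measured by the PedsQL 4.0 Total Scale Score". Protocol Section 7.8.3 says that the change "for the self-report and the parent-report will be summarized using descriptive statistics by visit".

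SAP Section 5.2 writes out formulas for rescue medication, headache duration and headache severity, and refers total headache days to the primary formula. It gives none for PedsQL. SAP Section 4 (definitions and derivations) has no PedsQL entry, and SAP Section 10 reports no departure from the protocol's planned analyses.

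**The concern.** Each item already carries a 0–100 score after transformation, so adding 23 of them cannot give a total on 0–100. The step that would bring it back, division by the number of items, is absent. With no formula in the available SAP text, Section 6.3 is the only scoring rule a programmer can follow, and it says to add.

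What is at stake is the reported size of a secondary endpoint. Section 6.3 presents the PedsQL as a tool for comparison across health conditions and with healthy children. A total on 0–2300 cannot be set beside results on 0–100 without rescaling. A sum also leaves open what happens when an item is blank, which a mean of answered items would settle.

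**Working it through.** **Inputs, all from Protocol Section 6.3**

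- Items per domain: 8, 5, 5 and 5.
- Raw responses 0 to 4, transformed to 100, 75, 50, 25 and 0.
- Rule for the total: the sum over all items.

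**Reproducing the plan's own figures**

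- Item count: 8 + 5 + 5 + 5 = 23, as stated.
- Transformation: 100 − 25 × raw gives 100, 75, 50, 25, 0, as stated. The form for ages 5–7 (Protocol Appendix 10.4) uses raw values 0, 2 and 4, which become 100, 50 and 0, so the limits are unchanged.

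**Range of the total under each reading**

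| Reading | Minimum | Maximum |
|---|---|---|
| Sum of transformed items (as written) | 23 × 0 = 0 | 23 × 100 = 2300 |
| Sum of reversed raw items | 23 × 0 = 0 | 23 × 4 = 92 |
| Mean of transformed items | 0 / 23 = 0 | 2300 / 23 = 100 |

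Of the three, only the mean gives 0–100.

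**Effect on a change score, complete forms.** Take a child who moves from 50 to 75 on every item. The sum goes from 23 × 50 = 1150 to 23 × 75 = 1725, a change of 575. The mean changes by 25. The ratio is 575 / 25 = 23. Standard deviations scale by the same constant, so direction, ranking and any standardised difference are unaffected.

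**Effect of one blank item, conditional on how blanks are handled**

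- *Sum over answered items only.* For a child at 75 on every item, the total falls from 1725 to 22 × 75 = 1650. The loss is 75, or 75 / 23 = 3.26 points on the 0–100 scale. For an item that would have scored 25, 50 or 100, the loss is 25/23 = 1.09, 50/23 = 2.17 or 100/23 = 4.35. A blank at follow-up would lower the change from baseline; a blank at baseline would raise it.
- *A blank makes the sum missing.* There is no downward shift, but the form contributes no total.
- *Mean of answered items.* 1650 / 22 = 75, unchanged.

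Neither document gives an item-level missing rate, so these are effects per blank item and not an expected bias for the trial.

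**The case against.** Four points can be made for the plan as it stands.

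First, the 0–100 range is grammatically attached to the transformed items. A reader might infer that Section 6.3 gives two conflicting ranges for the same total; it does not quite do that. This stands as a point of reading. But the sentence opens by saying how the total score is obtained, and if the range belongs only to the items, the total has no stated range and a rule that yields 0–2300. The definition needs completing on either reading.

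Second, a reader might infer that a blank item counts as the worst possible answer, because it would add 0 and 0 is the score for the worst response. The documents do not say this. It follows only if answered items are summed and blanks ignored; if a blank makes the total missing, the inference fails.

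Third, a reader might infer that the plan has no missing-item rule. That cannot be concluded. The SAP's table of contents lists Section 6.7.1, Missing Efficacy Data, and its summary of changes refers to Section 7.3, but neither text is in the public copy. A scoring or missing-item rule could be in either place. This objection stands in full, so the blank-item effect can only be stated conditionally.

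Fourth, the impact is small. The endpoint is summarised descriptively, the factor of 23 is constant on complete forms, and values above 100 would be noticed in the first output table. This limits the weight of the point but does not make the written rule correct.

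**Conclusion.** The point holds for the scoring rule. As written, Section 6.3 yields a Total Scale Score of 0–2300, and nothing in the available SAP text brings it back to 0–100. Reported means and changes would be 23 times the 0–100 scale for both self-report and parent-report. This is plain arithmetic on the protocol's own figures and needs no assumption.

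The blank-item effect is a possibility and not a finding: up to 4.35 points per blank item on the 0–100 scale if answered items alone are summed, and none if a blank makes the total missing.

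The primary analysis and the sample size are unaffected. The point is worth correcting before database lock because the endpoint is named in both documents and the correction is trivial. It does not threaten the trial's conclusions.

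The point concerns the Total Scale Score only. Section 6.3 does not say that the summary scores or sub-scores are sums, and the endpoint does not use them.

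**What to change.** In Protocol Section 6.3, replace the sum with a mean: the Total Scale Score is the sum of the transformed item scores divided by the number of items answered, with range 0 (worst) to 100 (best). Put the same formula in SAP Section 5.2, item 6, beside the formulas already given for the other secondary endpoints.

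Confirm that this agrees with the SAP's section on missing efficacy data. If a minimum number of answered items is to be required, the sponsor should state it before unblinding; the available text gives no such minimum, and none is proposed here.

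The cost is one sentence in each document and a check of the derivation program. No data collection, visit or sample-size figure changes.

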6.5 Safety Variables and Assessments

Investigators are responsible for monitoring the safety of subjects who have entered this study and for alerting Supernus or its designee to any event that seems unusual, even if this event may be considered an unanticipated benefit to the subjects.

Safety assessments include monitoring, evaluation, and recording of all concomitant medications, and the evaluation of AEs, clinical laboratory test results, vital signs, 12-lead ECGs, suicidality monitoring/C-SSRS results, the performance of physical and neurological examinations, and cognitive assessment as detailed in the Schedule of Events and Assessments (Table 2). Subjects will also be monitored for visual/ocular disturbances, nephrolithiasis, oligohydrosis, hyperthermia, metabolic acidosis (serum bicarbonate), hyperammonemia, and hepatic injury.

6.6 Adverse Events

As defined by the ICH Guideline for GCP, an AE is any untoward medical occurrence in a patient or clinical investigation subject who was administered a pharmaceutical product and which does not necessarily have to have a causal relationship with treatment.

An AE can be:

- Any unfavorable and unintended sign (including an abnormal laboratory finding), symptom, or disease temporally associated with the use of a medicinal product, whether or not considered related to the medicinal product.
- Any new disease, intercurrent injuries, or exacerbation of an existing disease.
- Any deterioration in a laboratory value or other clinical test (e.g., ECG) that results in symptoms, a change in treatment, or discontinuation from SM.
- Recurrence of an intermittent medical condition (e.g., muscle pain) not present at baseline.

Surgical procedures are not AEs; they are therapeutic measures for conditions that require surgery. The condition for which the surgery is required is an AE, if it occurs or is detected during the study period.

6.6.1 Causality

AEs may be categorized as either ADRs or SADR based on their relationship to SM and the degree of certainty about causality.

SADRs are a subset of AEs for which there is evidence to suggest a causal relationship between the drug and the AE, i.e., there is a reasonable possibility that the drug caused the AE.

ADRs are a subset of all SADRs for which there is reason to conclude that the drug caused the event.

6.6.2 Recording and Evaluation of Adverse Events

All subjects who provided written Informed Consent (Visit 1) and prior to randomization, will be questioned regarding the occurrence of AEs which will be captured as medical history. TEAEs are AEs that occur after study treatment has started, or an already present event that worsens either in intensity or frequency following the study treatment.

At each subsequent visit or contact with the subject, after the first administration of SM, the investigator must seek information on AEs by specific questioning and, as appropriate, by examination. Information on all AEs should be recorded immediately in the appropriate AE module of the eCRF. All clearly related signs, symptoms, and abnormal results for diagnostic procedures should be recorded in the source document, though they may be grouped under one diagnosis. For example, fever, elevated WBC count, cough, abnormal chest X-ray, etc., may be reported as a single AE of "pneumonia". The clinical course of each AE will be followed for at least 30 days after subject's early discontinuation/EOS, until resolution (AEs in general) or based on the medical judgment of the Investigator, the event has stabilized or is assessed as chronic.

The Investigator is responsible for evaluating AEs and determining the following:

- **Serious vs. Non-serious:** Is the event an SAE?
- **Causality:** Was AE related or not related to the SM?
- **Severity:** How pronounced is the incapacity/discomfort caused by an AE?

6.6.3 Criteria for Assessing Severity

The Investigator will evaluate the comments of the subject and the response to treatment in order that he or she may judge the true nature and severity of the AE. Severity refers to the accumulated intensity of discomfort/impairment of health since the last recording of AEs and will be assessed according to the following criteria:

- **Mild:** Awareness of sign, symptom, or event, but easily tolerated
- **Moderate:** Discomfort enough to interfere with usual activity and may warrant intervention
- **Severe:** Incapacitating with inability to do usual activities or significantly affects clinical status and warrants intervention

The criteria for assessing severity are different from those used for seriousness.

6.6.4 Criteria for Assessing Causality

The Investigator is responsible for determining the relationship between the administration of SM and the occurrence of an AE as not suspected or as a suspected reaction to SM. These are defined as follows:

Not suspected: The temporal relationship of the AE to SM administration makes a causal relationship unlikely, or other drugs, therapeutic interventions, or underlying conditions provide a sufficient explanation for the observed event.

- **Not related:** Temporal relationship to SM administration is missing or implausible, or there is an evident other cause.
- **Unlikely related:** Temporal relationship to SM administration makes a causal relationship improbable; and other drugs, chemicals, or underlying disease provide plausible explanations.

Suspected: The temporal relationship of the AE to SM administration makes a **causal relationship possible**, and other drugs, therapeutic interventions, or underlying conditions do not provide a sufficient explanation for the observed event.

- **Possibly related:** Temporal relationship to SM administration is plausible, but concurrent disease or other drugs or chemicals could also explain event. Information on drug withdrawal may be lacking or unclear. This will be reported as a **SADR**.
- **Definitely related:** Temporal relationship to SM administration is plausible, and concurrent disease or other drugs or chemicals cannot explain event. The response to withdrawal of the medication (dechallenge) should be clinically plausible. The event must be definitive pharmacologically or phenomenologically, using a satisfactory rechallenge procedure if necessary. This will be reported as an **ADR**.

6.6.5 Serious Adverse Events

AEs are classified as serious or non-serious. An AE or ADR is considered “serious” if, in the view of either the investigator or Sponsor, it results in one of the following outcomes:

- death
- life-threatening AE (i.e., the subject was at immediate risk of death from the AE as it occurred. This does not include an event that, had it occurred in a more severe form or was allowed to continue, might have caused death.)
- in-patient hospitalization or prolongation of existing hospitalization
- persistent or significant disability or incapacity or substantial disruption of the ability to conduct normal life functions
- a congenital anomaly or birth defect
- an important medical event

Important medical events are those that may not be immediately life threatening or result in death or hospitalization but are clearly of major clinical significance. They may jeopardize the subject and may require intervention to prevent one of the other serious outcomes noted above. For example, drug overdose or abuse, blood dyscrasias, a seizure that did not result in in-patient hospitalization or intensive treatment for allergic bronchospasm in an emergency department would typically be considered serious.

6.6.6 Investigator Responsibilities for Reporting SAEs

AEs will be followed for at least 30 days after subjects' early discontinuation/EOS or until resolution (AEs in general). SAEs will be followed until resolution or until no further/additional information can be obtained regarding the event.

The Investigator must immediately report to the Sponsor all SAEs, regardless of whether the Investigator believes they are drug related.

All SAEs must be reported to the Drug Safety Contact within 24 hours of first becoming aware of the SAE. The Investigator must complete an SAE Form and include a detailed description of the SAE, as well as other available information pertinent to the case (e.g., hospital records, autopsy reports and other relevant documents as applicable). The investigator will keep a copy of this SAE Report form on file at the study site.

The Investigator or study physician, after thorough consideration of all facts that are available, must include an assessment of causality of an AE to SM in the report to the Sponsor.

Follow-up information, or new information available after the initial report, should be actively sought and reported to the Sponsor, as it becomes available, using the SAE Report Form.

